# 7.4. Number of participants

Not applicable.

#### 7.5. Definitions of AIDs

Claims based algorithms obtained from the published literature defining AID conditions and are validated with demonstrated PPV will be used to identify AIDs. If participants meet >1 definitions, they will be included in multiple cohorts; AIDs will be analyzed separately.

## **SLE:**

≥1 inpatient claim with a diagnosis code for SLE (ICD-10 M32.1, M32.8, M32.9) OR ≥2 physician outpatient claims with SLE diagnosis during an office visit and/or emergency visit that were at least 30 days apart in the 365-day baseline period prior to the index date OR >1 rheumatologist visit/encounter/claim for SLE.

• The algorithm that includes ≥1 rheumatologist visit/encounter/claim has demonstrated a PPV of 95% and sensitivity of 83% [Hanly, 2014].

219111 (EPI-ZOSTER-097 VE US DB) Protocol Final

#### MS:

≥3 of any combination of inpatient diagnoses (any position) of MS (ICD-10 G35), ambulatory visit diagnoses of MS, emergency department (ED) diagnoses of MS, or MS-specific disease-modifying therapy fills/infusions (refer to Appendix 6 for medication categories) during the 365-day baseline period. At least one of these must be an inpatient, AV, or ED diagnosis of MS.

• This algorithm has demonstrated a PPV of 95-97% and sensitivity of 85-93% [Wallin, 2019].

#### IBD (CD and UC):

≥1 inpatient claim with a diagnosis code for CD (ICD-10 K50) and UC (ICD-10 K51) OR ≥2 physician outpatient claims with CD (ICD-10 K50) and UC (ICD-10 K51) diagnosis during an office visit and/or emergency visit that were at least 30 days apart in the 365-day baseline period prior to the index date.

- The algorithm that includes ≥2 physician outpatient claims with CD and UC diagnoses during an office visit and/or emergency visit has been used extensively in the literature though no PPV has been reported [Weng, 2007].
- Algorithms that have been published to classify mutually exclusive groups of UC and CD participants will be considered to differentiate between the two conditions [Pilon, 2020]. Participants will be identified as having UC if (i) they had more UC-related patient admissions than CD-related inpatient admissions; (ii) they had an equal number of UC- and CD-related inpatient admissions but more UC-related outpatient visits than CD-related outpatient visits; (iii) they had an equal number of UC- and CD-related inpatient admissions and outpatient visits. [Bernstein, 1999; Shaw, 2011].

#### RA:

≥1 inpatient claim with a diagnosis code for RA (ICD-10 M05, M06) OR ≥2 physician outpatient claims with RA diagnosis during an office visit and/or emergency visit that were at least 30 days apart in the 365-day baseline period prior to the index date.

• The algorithm that includes ≥2 physician outpatient claims with RA diagnosis during an office visit and/or emergency visit has been used extensively in the literature though no PPV has been reported [MacLean, 2000].

#### PsO:

 $\geq$ 1 inpatient claim with a diagnosis code for PsO (ICD-10 L40) OR  $\geq$ 2 physician outpatient claims with PsO diagnosis during an office visit and/or emergency visit that were at least 30 days apart OR  $\geq$ 1 dermatologist visit/encounter/claim for PsO in the 365-day baseline period prior to the index date.

• The algorithm that includes ≥1 dermatologist visit/encounter/claim has demonstrated a PPV of 90% and sensitivity of 88% [Asgari, 2013]. These algorithms assume PsO without PsA. Based on the rapid data queries (RDQs), 9% of participants diagnosed with PsO had PsA. In practice, rheumatologists tend to assess PsO and PsA by criteria which are unique to each. Then, they assess the 2 AIDs together in patients with symptoms of both. Sensitivity analyses will be performed on participants who

219111 (EPI-ZOSTER-097 VE US DB) Protocol Final

have either PsO or PSA, participants who have PsO only, participants who have PsA only, and participants who have both PsO and PsA to address the potential overlap between PsO and PsA. These analyses will be described in detail in the SAP.

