### 7. STUDY POPULATION

## 7.1. Description of population

The study population will include adults aged ≥50 YOA who are beneficiaries in the OptumTM database, diagnosed with an AID (defined as RA, IBD [UC or CD], SLE, PsO, PsA and MS), and who received RZV vaccination (along with their unvaccinated matches) anytime between 1 January 2018 to 31 December 2021 (Section 7.5 describes the algorithms for identification of AIDs). Co-existence of more than one AID can occur – while it is not required that each AID cohorts be mutually exclusive, overlap is expected to be minimal. Details of inclusion and exclusion criteria are defined in Sections 7.2 and 7.3.

Table 1 shows the demographic characteristics of beneficiaries in the OptumTM database diagnosed with RA, IBD, SLE, PsO, PsA and MS during the study period (2018-2021) based on the inclusion criteria (Section 7.2) and exclusion criteria (Section 7.3). Most of the beneficiaries with SLE (38.6%), PsA (38.9%), and MS (47.3%) were 50-59 YOA, while most of the participants with IBD (39.4%), RA (42.8%), and PsO (36.9%) were

219111 (EPI-ZOSTER-097 VE US DB)
Protocol Final

>70 YOA. Most of these beneficiaries were female while over 60% were white in all AID groups.

Table 1 Demographic characteristics of beneficiaries by AID condition\* during the study period (2018^-2021).

	SLE		IBD		RA		PsO		PsA		MS	
	N	%	N	%	N	%	N	%	N	%	N	%
Age at AID diagnosis (years)												
50-59												47.
	7740	38.6	11254	34.4	32130	30.5	22794	35.5	6194	38.9	10150	3
60-69												31.
	6086	30.4	8577	26.2	28028	26.6	17668	27.5	4968	31.2	6828	8
≥70												20.
	6224	31	12875	39.4	45029	42.8	23680	36.9	4747	29.8	4463	8
Sex												
Female												76.
	17665	88.1	18690	57.1	79127	75.2	34772	54.2	9314	58.5	16431	6
Male												23.
	2385	11.9	14016	42.9	26060	24.8	29370	45.8	6595	41.5	5010	4
Race /Ethnicity	1											
Asian	446	2.2	593	1.8	2331	2.2	1853	2.9	342	2.1	208	1
Black												10.
	3824	19.1	2796	8.5	13609	12.9	4440	6.9	930	5.8	2290	7
Hispanic	2492	12.4	2296	7	13491	12.8	5530	8.6	1505	9.5	1262	5.9
Multiple/Other/												
Unknown	1076	5.4	1529	4.7	5299	5	2944	4.6	760	4.8	972	4.5
White												77.
	12212	60.9	25492	77.9	70457	67	49375	77	12372	77.8	16709	9
Total	20050	-	32706	-	105187	-	64142	-	15909	-	21441	-

\*Table presents overall distribution of beneficiaries' characteristics by AID; no information on vaccination status (see Table 3).

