#### PsA:

 $\geq$ 1 inpatient claim with a diagnosis code for PsA (ICD-10 L40.5) OR  $\geq$ 2 physician outpatient claims with PsA diagnosis during an office visit and/or emergency visit that were at least 30 days apart OR  $\geq$ 2 rheumatologist visit/encounter/claim for PsA OR  $\geq$ 1 rheumatologist diagnosis code for PsA together with  $\geq$ 1 dermatologist diagnosis code for PsA in the 365-day baseline period prior to the index date.

• The algorithm that includes ≥2 rheumatologist visit/encounter/claim for PsA has demonstrated a PPV of 81% and sensitivity of 77% [Asgari, 2013]. These algorithms assume PsA without PsO. Based on the RDQs, 37% of participants diagnosed with PsA had PsO. Sensitivity analyses will be conducted to address the potential overlap between PsO and PsA as described above.

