## 11.3.5. Sensitivity analyses

Sensitivity analyses will be performed to assess if the occurrence of the COVID-19 pandemic has an impact on the effectiveness of the vaccine in participants who test positive for COVID-19 during the follow-up period. Methods to identify the COVID test result (i.e., PCR) and analyses to assess the impact of the pandemic on the VE will be described in the SAP. Sensitivity analyses will also be performed on participants who have either PsO or PSA, participants who have PsO only, participants who have PsA only, and participants who have both PsO and PsA to address the potential overlap between PsO and PsA. Further details of the sensitivity analyses will be described in the SAP.

219111 (EPI-ZOSTER-097 VE US DB) Protocol Final

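### The psoriasis code L40 as written contains the psoriatic arthritis code L40.5, which conflicts with the stated intent and with the protocol's own 9% and 37% overlap figures

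*Protocol*

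**What the plan says.** Section 7.5 builds the PsO cohort from three routes within the 365-day baseline: one "inpatient claim with a diagnosis code for PsO (ICD-10 L40", two physician outpatient claims at least 30 days apart, or one dermatologist claim. Appendix 13.4.1 gives the PsO code as L40.X.

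The PsA cohort has four routes: one "inpatient claim with a diagnosis code for PsA (ICD-10 L40.5", two physician outpatient claims at least 30 days apart, at least "2 rheumatologist visit/encounter/claim for PsA" (no spacing stated), or one rheumatologist code together with one dermatologist code for PsA.

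On the relation between the two conditions the protocol makes these statements:

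- Section 7.5, PsO: "These algorithms assume PsO without PsA". The rapid data queries found PsA in 9% of PsO patients.
- Section 7.5, PsA: "These algorithms assume PsA without PsO". In the same queries, "37% of participants diagnosed with PsA had PsO".
- Section 7.5, opening paragraph: a patient who meets several definitions enters several cohorts.
- Section 7.1: across the AID cohorts, "overlap is expected to be minimal".
- Section 11.3.5: sensitivity analyses cover either condition, "participants who have PsO only, participants who have PsA only", and both.
- Section 11.1: the descriptive queries used the section 7.5 algorithms.

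**The concern.** L40.5 is a subcode of L40, so every PsA claim is also a PsO claim unless it is carved out, and no section carves it out. A programmer who follows the written list would build a PsO cohort that takes in almost all of PsA. The text around the codes describes something else: two algorithms each meant to stand without the other condition, and a measured overlap of little more than a third of PsA.

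What is at stake is the composition of the cohort for primary objective 5, the content of the PsA-only sensitivity analysis, and whether the PsO-or-PsA objectives (secondary 2, 9 and 16) add anything to PsO alone. The feasibility counts in Tables 1 to 3 also need to describe the population that the code list will actually select.

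**Working it through.** **Step 1. Do the two reported overlaps agree?** Inputs: Table 1 totals, PsO 64,142 and PsA 15,909; overlaps of 9% and 37% from section 7.5. The protocol does not state the denominators of the percentages; the Table 1 totals are assumed.

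- From PsO: 0.09 × 64,142 = 5,773 (8.5% to 9.5% gives 5,452 to 6,093).
- From PsA: 0.37 × 15,909 = 5,886 (36.5% to 37.5% gives 5,807 to 5,966).

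The two counts agree within rounding. They describe one overlap group of about 5,800 people.

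**Step 2. What overlap do the written codes imply?** Taking the PsA routes in turn, with L40.5 counted as L40:

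| PsA route | Meets the PsO rule? |
|---|---|
| One inpatient claim | Yes |
| Two outpatient claims at least 30 days apart | Yes |
| Rheumatologist plus dermatologist code | Yes, through the dermatologist claim |
| Two rheumatologist claims only | Not if they miss the PsO spacing or visit rule and no other L40 claim qualifies |

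Only the last route can miss PsO, and the documents do not give its share. I assume 0 to 10% of PsA, so that 90 to 100% of PsA (14,318 to 15,909 people) would also be PsO. For the written codes to yield 37%, about 63% of PsA patients would have to qualify solely through that route.

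**Step 3. PsA share of the PsO cohort under the written codes.** It is not known whether the 64,142 already includes patients with L40.5 alone, so both cases are shown.

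- Already included: 14,318 / 64,142 = 22.3% to 15,909 / 64,142 = 24.8%.
- Not included: the union of the two conditions is 64,142 + 15,909 − 5,886 = 74,165. The share runs from 14,318 / 74,165 = 19.3% to 15,909 / 74,165 = 21.5%. At the low end, leaving patients who miss the PsO rule out of the denominator (64,142 + 14,318 − 5,886 = 72,574) gives 19.7%.

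The share is thus roughly 19 to 25%, against the stated 9%.

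**Step 4. PsA-only group.**

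- Stated overlap: 15,909 − 5,886 = 10,023 people, or 63% of PsA.
- Written codes: 0 to 1,591 people, or 0 to 10%.
- Two-dose recipients (Table 3, PsA N = 2,845), if they share these proportions: 0.63 × 2,845 = 1,792, against 0 to 285.

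**Step 5. PsO as a share of the PsO-or-PsA group.**

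- Stated overlap: 64,142 / 74,165 = 86%.
- Written codes: 72,574 / 74,165 = 98% up to 100%. If Table 1 already includes L40.5, 64,142 / 65,733 = 98% up to 100%.

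**Step 6. Can Table 2 show which codes the queries used?** If PsA were fully nested, the HZ rate in PsO without PsA would be (1,533 − 499) / (134,443 − 34,023) = 10.3 per 1,000 person-years, against 11.40 for PsO as tabulated. That is plausible, so Table 2 does not settle the question.

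**The case against.** The strongest reply is that this is a code-list clarification with an evident intent. Membership of several cohorts is openly allowed, the overlap is measured and reported, and sensitivity analyses are planned for it. That much stands, and it is why the point is not graded higher.

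It does not remove the conflict. The protocol itself fixes the codes, and details deferred to the SAP cannot refill a PsA-only group that the codes empty. The remark on minimal overlap in section 7.1 can fairly be read as a general comment on six conditions, but it does not fit a measured 37%.

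A reader might infer more than the documents support:

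- *That primary objectives 5 and 6 stop being distinct.* They would be nested. About 75 to 81% of PsO would still have no PsA, and objective 6 is unaffected because PsA is L40.5 whatever code PsO uses.
- *That the overlap analyses could not be run.* Only PsA-only nearly vanishes. PsO-only stays large (74,165 − 15,909 = 58,256, or 64,142 − 15,909 = 48,233 if Table 1 already includes L40.5), and the either-condition and both-conditions analyses can be run.
- *That the queries certainly excluded L40.5, so PsO would grow to about 74,200.* This is an inference. Section 11.1 says the section 7.5 algorithms were used, and the denominators of the 9% and 37% are not given.
- *That the higher HZ rate in PsA biases vaccine effectiveness (VE).* The PsA rate is 14.67 / 11.40 = 1.29 times the PsO rate. With equal follow-up per person, adding 10,023 people at 14.67 to 64,142 at 11.40 gives 11.84, a rise of about 4%. VE is one minus a hazard ratio from matched cohorts, so a higher baseline rate does not itself bias it, and no figure in the protocol shows that VE differs between the conditions.

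**Conclusion.** The point holds as a conflict between the written PsO codes and the protocol's own account of the population. The codes imply that nearly all of PsA falls within PsO, while the text says PsO is taken without PsA and reports 37% of PsA overlapping. The queries appear to have used a narrower PsO definition than the one on the page.

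Programmed as written, the codes would raise the PsA share of the PsO cohort from 9% to roughly 19 to 25%, shrink PsA-only from about 63% of PsA to a small remainder, and make the PsO-or-PsA cohort almost the same as PsO.

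These sizes rest on three assumptions: the percentages refer to populations like Table 1; 0 to 10% of PsA qualifies only through rheumatologist claims that miss the PsO rule; and, for the two-dose counts, vaccinated patients overlap in the same proportions. Severity: should-fix.

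**What to change.** 1. In sections 7.5 and 13.4.1, define PsO as L40.x excluding L40.5x and keep L40.5x for PsA. Patients with both kinds of code then remain in both cohorts, as the opening of section 7.5 allows.
2. Rerun the cohort counts under that definition. Confirm that the 9% and 37% overlaps and the counts in Tables 1 to 3 reproduce, and restate them if they do not.
3. Reword the sentence "These algorithms assume PsO without PsA". Excluding the code does not exclude patients who carry both kinds of code, so the sentence would still not be literally true.
4. In section 7.1, replace the remark on minimal overlap with the measured PsO/PsA overlap.

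The cost is one code-list line in two places, two reworded sentences and a rerun of counts. No participant is lost overall, since patients with L40.5 codes alone stay in the PsA cohort.

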#### PsA:

 $\geq$ 1 inpatient claim with a diagnosis code for PsA (ICD-10 L40.5) OR  $\geq$ 2 physician outpatient claims with PsA diagnosis during an office visit and/or emergency visit that were at least 30 days apart OR  $\geq$ 2 rheumatologist visit/encounter/claim for PsA OR  $\geq$ 1 rheumatologist diagnosis code for PsA together with  $\geq$ 1 dermatologist diagnosis code for PsA in the 365-day baseline period prior to the index date.

• The algorithm that includes ≥2 rheumatologist visit/encounter/claim for PsA has demonstrated a PPV of 81% and sensitivity of 77% [Asgari, 2013]. These algorithms assume PsA without PsO. Based on the RDQs, 37% of participants diagnosed with PsA had PsO. Sensitivity analyses will be conducted to address the potential overlap between PsO and PsA as described above.

# 7.6. Matching

For the primary objectives, once sub-cohorts for each AID condition are identified, participants meeting inclusion criteria who receive 2 doses of RZV at least 28 days apart at the index date will be matched exactly with unvaccinated participants on age category by 5-year increments (50-54, 55-59, 60-64, 65-69, 70-74, 75-79, ≥80) and AID-related medication category (mutually exclusive) based on current use at the index date within the same AID group. Medication categories will be based on the medication windows described in 13.6. For the secondary objectives, participants meeting inclusion criteria who receive 1 dose of RZV at the index date will be matched with unvaccinated participants by 5-year increments (i.e., 50-54 age grouping) and by AID-related medication category (mutually exclusive) based on current use at the index date. Matching will be done with replacement.

Following matching as described above, propensity scores based on the likelihood of receiving RZV dose 2 versus no RZV vaccination will be calculated using logistic regression models with RZV vaccination as the dependent variable and independent variables as outlined in Section 6.2 to select the 3 unvaccinated participants which are the closest to each vaccinated participant, to reach a ratio of RZV vaccinated to RZV unvaccinated of 1:3. Propensity scores will be calculated within each cohort defined by AID to balance measured confounders (details to be provided in the SAP) among patients receiving RZV dose 2 and comparator patients with no prior RZV vaccination. A second cohort of patients will be created to compare patients receiving RZV dose 1 to patients with no prior vaccination, using the same approach to calculate propensity scores within each cohort defined by AID based on the likelihood of receiving RZV dose 1 versus no RZV vaccination. An unvaccinated patient may serve as a comparator for both the dose 1 and dose 2 cohorts, although separate index dates will be applied.

Covariate balance will be assessed before and after applying propensity scores using standardized mean differences, with standardized differences of 0.2 suggestive of important imbalance [Austin, 2009a; Austin, 2009b]. Any covariate demonstrating imbalance after weighting, suggesting residual confounding, will be included as an

219111 (EPI-ZOSTER-097 VE US DB)
Protocol Final

additional covariate in the Cox proportional hazard models. The same approach will be used for the secondary analyses for 1-dose noting that propensity scores will be estimated at dose 1 and receipt of RZV dose 2 will be a censoring event.

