- 7. Healthy-user bias: Participants receiving RZV, or other vaccines may be healthier or have other behaviors leading to improved health compared to their unvaccinated matches. This bias may lead vaccinated participants to have lower rates of HZ in the study. The study will capture and adjust for variables related to healthy users, such as use of other vaccinations, to minimize this bias.
- 8. Duplicate health care claims: A beneficiary of OptumTM may be a beneficiary of more than one insurance product at a time or switch to a new insurance product before departing from another, resulting in duplicate health care claims and multiple lines per participant. Also, when time periods overlap, a clean link between claims and the eligibility table may be absent because multiple rows may be returned in a match. While there is a risk of this happening, the number of multiple health care claims and their impact is expected to be negligible.
- 9. Limited follow-up period: While the ability to assess durability of VE at extended time points is limited, this is an open cohort study that will allow vaccinated and unvaccinated participants to come in late or die during the follow-up period; this is not expected to impact the overall incidence rate of HZ. In addition, participants entering the cohort in early 2018 could have 4 years of follow-up.
- 10. Generalizability: The population in OptumTM have racial/ethnic diversity, and the age distribution of participants with selected AIDs in this claims database are expected to reflect the distribution nationally. The practices of care for participants with selected AIDs are expected to be largely standardized across U.S. health care systems. However, this is a claims database and only the insured and beneficiaries who have Supplementary Medicare will be included in the database.

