# 11.3.2. Primary analyses

For the primary objectives 1-6, the number of incident HZ cases and the number of person-years of follow-up for participants will be assessed for the 2-dose ( $\geq$  28 days apart) RZV cohort and the matched unvaccinated cohort. Crude VE (%) will be estimated as (1 – [incidence rate of HZ among 2-dose (at least 28 days apart) RZV recipients / incidence rate of HZ among RZV unvaccinated participants]) x 100%.

Adjusted HRs and 95% confidence intervals (CIs) comparing HZ incidence rates in the 2-dose ( $\geq$ 28 days apart) RZV cohort, and the matched unvaccinated cohort will be estimated by Cox proportional hazards regression models. Estimates of VE (%) will be calculated as (1 – adjusted HR) × 100%.

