#### 11.3.3. Descriptive analyses

The number and characteristics of participants in each cohort will be described and compared. Categorical variables such as gender will be presented as absolute numbers and percentages with p-values for the Pearson  $\chi^2$  test or Fisher's exact test, as appropriate. Continuous variables such as age in years will be presented as the mean with standard deviation and/or median with interquartile ranges, with p-values for the two-sample t-test or Wilcoxon rank-sum test, as appropriate. Absolute standardized differences will be calculated to assess the balance of covariates with a cut-off value of 0.20. Overall incidence rates of HZ for the 2-dose ( $\geq$ 28 days apart) and the 1-dose RZV vaccinated cohort and the matched unvaccinated cohort will be calculated by dividing the number of HZ cases by the total number of person-years.

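### The primary Cox model gains a covariate when its post-matching standardized difference reaches 0.2, one covariate at a time; no fixed adjustment set is stated, so smaller same-direction residuals are left to matching alone

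*Protocol*

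**What the plan says.** Protocol 7.6 controls confounding in three layers.

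1. Exact matching on 5-year age band and AID medication category, within each AID.
2. A logistic propensity score on the listed covariates (7.6 points to 6.2, which points to the list in 6.3), used "to select the 3 unvaccinated participants which are the closest to each vaccinated participant", with replacement.
3. A balance check, "with standardized differences of 0.2 suggestive of important imbalance", with the consequence: "Any covariate demonstrating imbalance after weighting, suggesting residual confounding, will be included as an" "additional covariate in the Cox proportional hazard models".

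Section 11.3.3 repeats the threshold: "Absolute standardized differences will be calculated to assess the balance of covariates with a cut-off value of 0.20". Section 11.3.2 says that adjusted HRs "will be estimated by Cox proportional hazards regression models" but lists no covariates. On healthy-user bias, 5.2.1 item 7 states: "This bias may lead vaccinated participants to have lower rates of HZ in the study". It then commits the study: "The study will capture and adjust for variables related to healthy users, such as use of other vaccinations, to minimize this bias".

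**The concern.** VE here comes from a non-randomised comparison, so it depends on how well measured confounding is controlled. The third layer decides covariate by covariate. A set of differences all below 0.2 passes as balanced even if they all lean towards healthier vaccinees: more influenza vaccination, more preventive visits, fewer comorbidities. Section 5.2.1 names that direction and says that it lowers HZ among vaccinees, so such residuals would raise VE.

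Two features add to this. The covariates in the model may differ between the six AID cohorts according to which variables happen to cross the line. And residual bias does not shrink as the cohort grows, so a given bias matters most where the CI is narrowest (RA, PsO).

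**Working it through.** The cut-off of 0.2 is a convention, so there is no derived figure to reproduce. The check is how much bias it can let through.

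**Assumptions not in the protocol.** Binary risk factor; prevalence in comparators p0 = 0.1, 0.3 or 0.5; HZ rate ratio RR = 1.25, 1.5 or 2; vaccinees healthier.

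**Formulas.** Solve d = (p0 − p1)/√{[p0(1−p0) + p1(1−p1)]/2} for p1. The HR is then multiplied by B = [1 + p1(RR−1)]/[1 + p0(RR−1)]. Apparent VE = 1 − (1 − VE)·B. For k independent covariates in the same direction, use B^k.

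**One covariate just under the cut-off, d = 0.19.**
- p0 = 0.5, RR = 2: p1 = 0.406 and B = 1.406/1.5 = 0.937. True VE 50% reads 53.1%; true VE 0% reads 6.3%.
- Smallest effect on the grid (p0 = 0.1, RR = 1.25): B = 0.988; VE 50% reads 50.6%.
- Largest effect (p0 = 0.3, RR = 2): B = 0.936; VE 50% reads 53.2%.

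**Three such covariates, same direction.** B³ runs from 0.964 to 0.821, so VE 50% reads 51.8% to 59.0%. At the top end, VE 0% reads 17.9%.

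**Smaller differences.**

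| d | VE 50% reads, one covariate | three covariates, worst case |
|---|---|---|
| 0.19 | 50.6% to 53.2% | 59.0% |
| 0.10 | 50.3% to 51.7% | 55.0% |
| 0.05 | 50.2% to 50.9% | 52.6% |

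**Against precision.** Expected events use Table 2 rates and Table 3 numbers and mean follow-up, at VE 50% and 1:3. SE(log HR) = √(1/e1 + 1/e0), with e1 vaccinated and e0 comparator events.
- RA: e1 = 15928 × 1.4 × 0.01553 × 0.5 = 173; e0 = 3 × 15928 × 1.4 × 0.01553 = 1039; SE 0.082.
- PsA: e1 = 2845 × 1.3 × 0.01467 × 0.5 = 27; e0 = 163; total 190; SE 0.207.
- By the same steps, MS has 30 + 182 = about 213 events and SLE 32 + 193 = 225.

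Coverage of a nominal 95% CI = Φ(1.96 − |k·ln B|/SE) − Φ(−1.96 − |k·ln B|/SE). In RA with B = 0.937, this is 88% for one covariate and 34% for three. At d = 0.05 (p0 = 0.5, RR = 2, B = 0.983) it is 94.5%. The SE treats comparators as distinct people. Matching is with replacement, so the true SE is larger and these formulas overstate the loss of coverage.

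**What the planned matching would probably leave.** Tables 2 and 3 give 4.1 (IBD: 24,234/5,865) to 6.5 (MS: 20,407/3,121) unvaccinated people per vaccinee. A simulation of exact strata plus 1:3 nearest-score selection with replacement was run at these cohort sizes. It assumed 12 correlated binary covariates, 35 strata, a correctly specified score, log-odds for vaccination of 0.2 or 0.5 per covariate, and one run per setting. The largest single post-match difference was 0.03 to 0.07. Runs for PsA, SLE and IBD that included a misspecified score gave about the same.

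**The case against.** The strongest defence is that confounding is controlled by design and the 0.2 rule is only a backstop. An HR from a propensity-matched sample is already an adjusted estimate, so 5.2.1 item 7 can be read as met. This stands. A reader might infer that the covariates go unadjusted, or that 7.6 contradicts 5.2.1; the protocol supports neither reading. Section 7.6 also never says that only imbalanced covariates enter the model. Section 6.2 allows the variables as covariates where appropriate, and the SAP, not shown here, may list model terms.

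Close matching on a score also pushes the weighted sum of imbalances towards zero, so three predictors of vaccination all at 0.19 in the same direction is the pattern it tends to remove. The simulation agrees. The rate ratio of 2 is likewise only an assumption: the protocol gives none for influenza vaccination or preventive visits. Its twofold figure for SLE compares a disease with the general population, not covariate levels within a cohort.

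Finally, 0.2 is referenced in 7.6, and 0.1 is another convention that nothing in the protocol prefers.

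What remains is narrower. The protocol itself fixes the threshold and the data-dependent entry rule, so an SAP that follows it without adding a fixed set inherits both. Choosing the closest comparators does not guarantee small differences, and the backstop does not act until 0.2.

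**Conclusion.** The point holds as a cheap improvement, not as an error certain to bias VE. As written, 7.6 and 11.3.3 leave post-matching differences below 0.2 to the matching alone, and no covariate set is stated to enter the primary Cox model regardless of balance.

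Under assumed rate ratios of 1.25 to 2, one covariate just under the threshold moves a VE of 50% by about 0.6 to 3 points. At about 0.05 the shift is about 1 point or less. It would be tempting to conclude that VE will be inflated to 59%, or that RA coverage will fall to 34%. The protocol does not support this: those figures need three independent covariates at 0.19 in one direction and an SE that ignores comparator reuse. They are an unlikely upper limit. The actual post-match differences are unknown.

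**What to change.** - **7.6 and 11.3.2:** state that each primary Cox model adjusts for the Section 6.3 covariates applicable to that AID, whatever their standardized difference. In the smaller cohorts (SLE, MS, PsA), use the logit of the propensity score plus any covariate with a difference above 0.1. Show the matched HR without covariates alongside.
- **7.6 and 11.3.3:** use 0.1 as the balance flag. On its own this lowers the worst three-covariate reading of a 50% VE from 59% to 55%, so it complements fixed adjustment and does not replace it.
- **7.6:** replace the reference to weighting by matching, which is the method described.

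The cost is wording and a few lines of code; the covariates are already to be extracted. CIs may widen slightly, and some covariates may need collapsing where events are few (about 190 to 225 expected in PsA, MS and SLE at VE 50%). The gain is removal of measured residual confounding, if the model form is right, and a covariate rule set in advance for each AID.
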